**Study Measurements and weights**

All clinical data will be collected on standardized case report forms.

The Case Report Form will be used to collect all patient data and assessments that will be used for evaluation of the patient's response to treatment. It is the responsibility of the PI to ensure the completeness and accuracy of case report forms. One set of case report forms should be completed for each subject participating in the trial. The Case Report Forms should be completed within two (2) days of the patient's visit for review by Clinical Research Monitors, Inc., CCRP Pharmaceutical's agent for monitoring the trial. Case Report Forms will be monitored following guidelines established by CCRP Pharmaceuticals at the study onset. Investigators will permit inspection of the study files and patient medical charts by authorized representatives of Clinical Research Monitors & CCRP Pharmaceuticals and responsible government agencies.

Data will be entered at the site by the Principal Investigator (PI) and/or his/her designee. After all data has been entered and all queries are resolved for a patient, the patient's data will be locked. Once the data is locked, the PI will review the patient's data and will attach an electronic signature to the e-crf indicating that he/she has reviewed all data and to the best of his/her knowledge, the data has been accurately captured. It will be necessary for the PI to have on file at the FDA a certification statement that his/her electronic signature is 'intended to be the legally binding equivalent of traditional handwritten signatures.'

All proposed publications and presentations by investigators must be submitted to CCRP Pharmaceuticals for review and approval. A copy of each proposed publication and presentation

shall be submitted at least sixty (60) days prior to submission for publication or presentation. This provision is in recognition of CCRP Pharmaceutical's rights and responsibility to provide peer input regarding the content and conclusions of such publications and to ensure that none of its confidential information will be disclosed or inappropriately utilized.

### **Maintaining of Records**

Investigators shall maintain the records of drug disposition, Case Report Forms and other study records and worksheets for a period of 5 years following the date the Product License Application is approved by the FDA or, if the application is not filed or is withdrawn for 5 years after the Food and Drug Administration has been notified by CCRP Pharmaceuticals that the investigational program has been discontinued. To avoid error, investigators should contact CCRP Pharmaceuticals before the destruction of any records pertaining to the study to ensure they no longer need to be retained. In addition, CCRP Pharmaceuticals should be contacted if the investigator plans to leave the institution so that arrangements can be made for transfer of records.

Upon completion or termination of the study, investigators should submit a final written report to the sponsor as required by the U.S. IND regulations. The report should be submitted to CCRP Pharmaceuticals within 30 days of completion or termination of the study. This report should include:

1. Introduction: a brief description of the study.
2. Methods: a description of the methods employed and any deviations from the protocol.
3. Study Population: a statement of the number of patients evaluated; of the number of dropouts and reasons for them; and description of the initial nature and severity of medical conditions for which the patients were evaluated.
4. Results and Discussions: a clinical assessment of the effect of the investigational agent on the medical conditions evaluated and a description of adverse reactions observed or reported with an indication, to the extent possible, of their relationship to the investigational agent.
5. Conclusion: a summary statement of the investigator's opinion of the efficacy of the study agent in the patients enrolled in his/her study.

## **VIII. STATISTICAL METHODS**

The microbiological eradication rates and clinical response rates will be compared for Drug A and Cefuroxime axetil. A Chi-square analysis will be performed to compare the rates of eradication and response between the two drugs. Using an alpha level of 0.05 and power of 85% will require a sample size of 200 subjects in each of the two groups.

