**Drug A Protocol Summary**  
**Protocol No. NDP- 1 003**

- 1. Project Status:** Phase III
- 2. Purpose:** To evaluate the safety and efficacy of Drug A versus cefuroxime in the treatment of community acquired pneumonia
- 3. Design:** Multicenter, prospective, randomized Phase III study
- 4. Number of Subjects:** Approximately 450 outpatient subjects to yield 400 subjects that met the criteria, minimum of 200 subjects in each of two treatment groups. 20 subjects will be enrolled from each site
- 5. Types of Subjects:** Male and female subjects with clinical symptoms of community-acquired pneumonia who are appropriate candidates for oral therapy
- 6. Key Inclusion Criteria:** Subject must be at least 18 years old with clinical signs and symptoms of acute pneumonia
- 7. Key Exclusion Criteria:** Subjects infected with a known resistant organism; acute allergic reaction to any non-antimicrobial, or a severe reaction to penicillin or any cephalosporin; renal failure; neutropenia; pregnant or nursing mothers; prior use of an investigational agent within 30 days; or previous treatment under this protocol
- 8. Comparative Agent:** Cefuroxime axetil
- 9. Dosage & Duration:** Drug A - 500 mg PO q12h x 7-14 days Cefuroxime axetil - 500 mg PO q12h for 7-14 days
- 10. Safety Parameters:** Safety evaluations will be based on changes in the physical exam and laboratory tests from pre- to post-therapy and reporting of any adverse events.
- 11. Efficacy Parameters:**
  - a. Microbiological response (2-4 days post-therapy) will be based on eradication of the pathogens isolated at admission.
  - b. Clinical response (2-4 days post-therapy) will be based on resolution of signs/symptoms and changes in radiological findings reported at admission.
- 12. Location:** Multicenter; 20-25 sites are expected to participate
- 13. Data Analysis:**

- a. Safety - adverse events and changes in physical examinations and clinical laboratory tests from pre- to post-treatment will be summarized
- b. Efficacy- the microbiological eradication rates and clinical response rates will be compared for Drug A and Cefuroxime axetil

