## **1. BACKGROUND AND RATIONALE**

Drug, A is an investigational compound in the quinolone class of antibiotics. It- has been used in Europe for 5 years for treating patients with community-acquired bacterial pneumonia, with success rates around 90%.

Although Drug A is more active in vitro than other members of its class, toxicity profiles in animal studies are similar. Accordingly, Drug A is expected to offer an opportunity to enhance the efficacy profile of quinolones without an incremental increase in adverse events.

It is anticipated that Drug A could be used once daily for many infections including mild to moderate skin, lower respiratory, and pelvic infections, as well as UTIS. Severe or life-threatening infections could be treated with a twice-daily dosing schedule.

To date, approximately 150 subjects have received Drug A in Phase I and Phase II trials in the United States. Adverse reactions were judged probably or possibly drug-related in 14.8% of courses; drug treatment had to be stopped prematurely in 3.5%. The most frequent reactions were gastrointestinal complaints (chiefly nausea, diarrhea, and vomiting), metabolic disorders (elevated SGOT, SGPT, serum creatinine or blood urea nitrogen), nervous system effects (dizziness, restlessness, tremor, and headache), and rash.

In animal toxicologic trials, Drug A and other quinolones appear to have similar safety profiles. The absorption, distribution, metabolism, and excretion appear to be similar as well, both in animals and in humans. Based on these studies, it is anticipated that the fate of administered Drug A will be comparable to that of other long acting quinolones both with respect to human safety and tolerance.

Over 40 million people have been treated with various quinolones. They have generally been well tolerated. The events considered likely to be drug-related in clinical trials in subjects receiving multiple doses were nausea, headache, dizziness, and diarrhea.

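### Section VIII powers a chi-square test of difference against an active comparator without stating a hypothesis, rates, target difference or margin; if the aim is comparability, a non-significant result cannot show it

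*Protocol*

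**What the plan says.** Protocol, section VIII (Statistical Methods), opens with the comparison: "The microbiological eradication rates and clinical response rates will be compared for Drug A and Cefuroxime axetil". It then names the test: "A Chi-square analysis will be performed to compare the rates of eradication and response between the two drugs". The sample size follows in one sentence: "Using an alpha level of 0.05 and power of 85% will require a sample size of 200 subjects in each of the two groups".

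The Protocol Summary, the Objective and the Description of Study all describe an evaluation of Drug A against cefuroxime axetil, an active drug. None of them uses the words superiority, non-inferiority or equivalence. None gives a cefuroxime response rate, a difference to be detected or a margin.

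The only success rate in the document is in section 1 (Background and Rationale), where European use of Drug A in community-acquired bacterial pneumonia is reported "with success rates around 90" percent. The only efficacy gain that section anticipates is over other quinolones. It makes no claim against cefuroxime.

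**The concern.** A chi-square test can reject equality of two rates, but it cannot establish that they are close. A large p-value arises when the drugs perform alike, and also when one is somewhat worse and the trial is too small to show it. Since the Protocol offers no reason to expect Drug A to beat cefuroxime, a reader may take the aim to be comparable efficacy. Under that aim, the planned test can end without supporting the conclusion the trial was run to reach, and a real deficit could be read as no difference.

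The power sentence has a related defect. Alpha, power and the type of test do not determine a sample size for two proportions; the two rates are needed as well. Without them nobody can tell what size of difference the 85% refers to.

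**Working it through.** **Inputs from the Protocol.** n = 200 per group, alpha 0.05, power 85%, chi-square test (section VIII); equal allocation (Randomization); Drug A success about 90% (section 1).

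**Assumptions.** The test is two-sided, as a 2×2 chi-square normally is. The 90% is used as a reference rate only because it is the sole rate given. It describes Drug A in Europe; applying it to cefuroxime is an assumption.

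**1. Can 200 per group be reproduced?** No, because the rates are missing. The gap that gives 85% power has to be solved for instead. With pooled variance, d = |p1 − p2| and p̄ = (p1 + p2)/2:

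power = Φ{ [d√n − 1.96√(2p̄(1−p̄))] / √(p1(1−p1) + p2(1−p2)) }

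- 90% v 80%: [0.10 × 14.142 − 1.96 × √0.255] / √0.25 = (1.414 − 0.990)/0.5 = 0.849, so power is 80.2%. Reaching 85% would need 228 per arm.
- 90% v 79.2% (gap 10.8 points): power 85%.
- 90% v 97.3% (gap 7.3 points, with 90% as the lower rate): power 85%.

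Gap below other reference rates that gives 85% power at 200 per arm:

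| Reference rate | Gap (points) |
|---|---|
| 95% | 8.7 |
| 90% | 10.8 |
| 85% | 12.2 |
| 80% | 13.2 |
| 50% | 14.8 |

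So the gap runs from about 7 to 15 points. At the 90% reference it becomes 9.5 points one-sided and 11.4 points with continuity correction.

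**2. How often would the test be non-significant?** Exact binomial calculation for the uncorrected chi-square, 200 per arm, cefuroxime assumed at 90%:

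| True Drug A rate | Deficit (points) | P(non-significant) |
|---|---|---|
| 90% | 0 | 95% |
| 85% | 5 | 67% |
| 83% | 7 | 46% |
| 82% | 8 | 36% |
| 80% | 10 | 19% |

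A single data set shows the same thing. With 180/200 on cefuroxime and 167/200 on Drug A, the observed deficit is 6.5 points and z = 1.92, which is not significant. The upper 95% limit for the deficit is 6.5 + 1.96 × √(0.90 × 0.10/200 + 0.835 × 0.165/200) = 13.1 points.

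**3. What would an interval from the same patients give?** Half-width = 1.96 × √{[p1(1−p1) + p2(1−p2)]/200}:

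- 90% v 90%: 5.9 points
- 90% v 85%: 6.5 points
- 90% v 82%: 6.8 points
- 90% v 80%: 6.9 points

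Non-inferiority power when both true rates equal p, with margin M and one-sided 0.025, is Φ(M/SE − 1.96), where SE = √(2p(1−p)/200). The 10-point margin is only an illustration, since the Protocol gives none.

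| Common rate | SE | Power, M = 10 points | n per arm for 85% at M = 10 | M giving 85% at 200 per arm |
|---|---|---|---|---|
| 90% | 0.0300 | Φ(1.37) = 91.5% | 162 | 9.0 points |
| 85% | 0.0357 | Φ(0.84) = 80.0% | 229 | 10.7 points |
| 80% | 0.0400 | Φ(0.54) = 70.5% | 288 | 12.0 points |

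**The case against.** The Protocol says only that the drugs will be evaluated and compared; it never claims comparability. A chi-square test against an active comparator is a legitimate superiority test. This stands: comparability is inferred from the absence of any claimed advantage over cefuroxime, and the test is not wrong in itself.

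An analysis plan that is not shown may add a confidence interval, and the absence of one from a protocol would not be a finding by itself. That also stands. It does not rescue the sample-size sentence, because section VIII fixes both the number and the power without the inputs that produce them. A margin introduced later would change the hypothesis for which the trial was sized.

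Three stronger readings are tempting, and the documents do not support them:

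- **That 200 per group is wrong, or that the power holds only for 11 points.** The 10.8-point gap depends on taking 90% as the higher rate. Other assumptions give roughly 7 to 15 points, and the power also holds for anything larger. Nor does the Background define success, so its 90% may not match this trial's response categories.
- **That the trial would answer nothing.** The same data yield an interval that is informative about the difference. The weakness lies in the decision rule, which is built on the test.
- **That a worse Drug A would usually pass unnoticed.** On the assumed 90%, this is so at 5 points (67%) but no longer at 7 points (46%). A 5- or 8-point deficit would also lie inside a 10-point margin.

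**Conclusion.** The point holds in a bounded form. Section VIII names a test of difference against an active drug as its only efficacy analysis and states 85% power with no hypothesis, rates, difference or margin. If the aim is comparability, a non-significant result cannot support it: with cefuroxime assumed at 90%, that result occurs about 95% of the time under equality and still 67% of the time with a true 5-point deficit. If the aim is superiority, the test is suitable, but the power claim lacks its target difference. In both cases the sample size is uncheckable, which is different from being shown to be too small or too large. The non-significance figures rest on the assumed 90% rate, 200 evaluable subjects per arm and a two-sided test.

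**What to change.** In section VIII, state the hypothesis first, then match the analysis and sample size to it.

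- **If comparability is the aim:** base the efficacy comparison on the two-sided 95% confidence interval for the difference in response, Drug A minus cefuroxime. Conclude non-inferiority if the lower limit lies above a pre-set negative limit (minus the margin) that the sponsor justifies, and superiority if it lies above 0. State the assumed rates, the margin and the resulting power.
- **If superiority is the aim:** keep the chi-square and restate the power with its rates, for example 85% for about 90% v 79%, or 80% for 90% v 80%.

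Make the change before any outcome data are seen, because a margin chosen afterwards carries little weight.

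**Cost.** The same patients and data are used, and the text change is confined to section VIII. The sponsor does have to justify a margin, and the stated power may not survive. With a 10-point margin, 200 per arm falls below 85% if response is 85% or 80%; keeping 85% power would then need 229 or 288 per arm, or a wider margin that can be defended.

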## 2.2 SUBJECT SELECTION

### A. Study Population

To ensure clinically evaluable data from 400 subjects (a minimum of 200 subjects in each of two treatment groups), approximately 450 outpatient subjects with community-acquired pneumonia will be admitted to the study.

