## **E. Randomization**

As subjects qualify for the study, subject numbers will be assigned in strict sequential order at each site. Subjects will receive one of two treatment regimens according to a computer-generated randomization schedule prepared by the CCRP Pharmaceuticals, Inc. and kept at the individual investigational sites. This randomization schedule will provide for equal numbers of subjects in the two regimens. The random study group assignment will be provided for each subject in individually sealed envelopes. As a qualified subject enters the study, the next available randomization envelope in the sequence will be opened to reveal the appropriate therapy regimen. The following two regimens will be used:

- 1. Drug A 500 mg PO q12h**
- 2. Cefuroxime axetil 500 mg PO q12h**

Total therapy duration will be 7 to 14 days, as clinically indicated. A minimum of five days of therapy will be required for analysis of microbiologic response, unless subjects have failed clinically and have taken sufficient drug to be considered evaluable within this time. If, in the opinion of the investigator, a subject requires more than 14 days of therapy (e.g., *Legionella pneumophila*, slowly resolving pneumonia, etc.) the medical monitor should be contacted.

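### One 85% power figure and one 200 per group serve two endpoints, neither named primary, and the power cannot hold for eradication, which only culture-positive subjects can enter

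*Protocol*

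**What the plan says.** Section VIII sets two comparisons: "The microbiological eradication rates and clinical response rates will be compared for Drug A and Cefuroxime axetil". The method is the same for both: "A Chi-square analysis will be performed to compare the rates of eradication and response between the two drugs". The sample-size sentence follows at once: "Using an alpha level of 0.05 and power of 85% will require a sample size of 200 subjects in each of the two groups". It names no endpoint, assumed rates, difference or sidedness. Protocol Summary items 11 and 13 list the two endpoints side by side, and nothing in the protocol calls either one primary.

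**Who the 200 are.** Section 2.2 A, Study Population, gives the purpose of enrolling about 450: "To ensure clinically evaluable data from 400 subjects (a minimum of 200 subjects in each of two treatment groups". The Description of Study ends the trial on that same count of clinically evaluable subjects.

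**Who can enter the eradication analysis.** Summary item 11 says "Microbiological response (2-4 days post-therapy) will be based on eradication of the pathogens isolated at admission". None of the six inclusion criteria in section 2.2 B is a positive culture. The Visit 1 procedures require a respiratory specimen, not growth of a pathogen. Section 2.2 E adds "A minimum of five days of therapy will be required for analysis of microbiologic response", and the same sentence exempts clinical failures who have taken enough drug to be evaluable.

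The Description of Study also allows an amendment to secure enough subjects with critical pathogens. It gives no number and no trigger.

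**The concern.** The two endpoints have different denominators but share one sample-size statement. The 200 per group are counted by clinical evaluability, and the step from 450 to 400 allows only for losses on that count. Subjects with no pathogen at baseline count towards the 200 but contribute nothing to eradication.

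Two things are at stake. First, a reader of section VIII would expect 85% power for the eradication comparison and would probably not get it, so a null result there could be misread. Second, with no primary endpoint and no success rule, it is open which result supports the efficacy claim. The error rate and the power of the trial as a whole depend on that choice.

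**Working it through.** **1. Can the 200 be reproduced?** Not from the protocol, because it gives no rates and no difference. It can only be solved backwards. The one rate available is in section 1, where European experience with Drug A is described "with success rates around 90" percent. That is a background success rate, not a stated sample-size input, so its use here is an assumption.

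Formula (two proportions, pooled variance under the null, two-sided 0.05, no continuity correction), with p̄ the mean of p1 and p2:

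power = Φ{ [ |p1 − p2|·√n − 1.960·√(2p̄(1 − p̄)) ] / √(p1(1 − p1) + p2(1 − p2)) }

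With n = 200 and p1 = 0.90, 85% power needs p2 = 0.7923, a difference of 0.1077:
- p̄ = 0.84615; 1.960 × √0.2604 = 1.000
- √(0.0900 + 0.1646) = 0.5045
- 0.1077 × √200 = 1.523
- (1.523 − 1.000) / 0.5045 = 1.037, and Φ(1.037) = 0.85

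Other starting points fit as well. From 85% the detectable lower rate is 72.8% (12.2 points), and from 80% it is 66.8% (13.2 points). One-sided from 90%, it is 80.5% (9.5 points). So 200 does not identify the effect the sponsor had in mind.

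**2. Power for eradication by culture yield.** Yield means the share of the 200 who have a baseline pathogen and are microbiologically evaluable. The protocol does not give it, so the range is assumed. The effect is held at 90% vs 79.2%.

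| Yield | n per arm | Power | Difference detectable with 85% power |
|---|---|---|---|
| 30% | 60 | 37% | 22.0 points |
| 50% | 100 | 56% | 16.2 points |
| 70% | 140 | 71% | 13.3 points |
| 90% | 180 | 81% | 11.4 points |
| 100% | 200 | 85% | 10.8 points |

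Example at 50%: (0.1077 × √100 − 1.000) / 0.5045 = 0.152, and Φ(0.152) = 0.56.

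**3. Does the choice of rates drive this?** Hardly. If 200 per arm gives 85% power for some difference, power for the same difference at yield f is roughly Φ[(1.960 + 1.036)·√f − 1.960]. For f = 0.3, 0.5 and 0.7 this gives Φ(−0.319) = 0.375, Φ(0.158) = 0.563 and Φ(0.547) = 0.708. The loss depends mainly on the yield.

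**4. Yield needed to keep 85%.** 200/200 = 100% of clinically evaluable subjects. Even if everyone enrolled counted, it would be 400/450 = 89%. At a 50% yield, 200/0.5 = 400 clinically evaluable subjects per arm would be needed.

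**5. Two endpoints, no rule.** If either could carry the claim and the tests were independent, the chance of at least one false positive is 1 − 0.95² = 9.75%. Positive correlation lowers it, and it cannot exceed 0.05 + 0.05 = 10%. If both had to succeed, there is no such inflation, but joint power cannot exceed the smaller of the two powers. On the illustration above, that caps it at 37%, 56% or 71%.

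**The case against.** The strongest reply is that section VIII never says the 85% is for eradication. Sections 2 and 2.2 A tie the 200 to clinically evaluable subjects, so the trial may have been sized on clinical response, with nothing promised for eradication. That is a fair reading, and it means an explicit false power claim for eradication is not proven. It does not remove the problem. The power sentence directly follows a test of both rates, no other size is given and no endpoint is excluded, so the text has to say which one the 200 serves. Eradication could also have 85% power at a lower yield if its true difference were larger, but no separate effect is stated for it.

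Four further inferences are tempting, and the protocol does not support them:
- **That the eradication denominator is selected on outcome**, because cured subjects may produce no sputum at Visit 3. The protocol schedules a post-therapy culture for everyone, accepts several specimen types at baseline and does not say that subjects without a specimen are dropped. Scoring of missing specimens may properly sit in the SAP, which is not shown.
- **That five days of therapy is an absolute requirement.** Evaluable clinical failures are exempt.
- **That the trial's error rate is 9.75%.** This follows only if either endpoint alone can carry the claim, which the protocol does not say. A multiplicity procedure may also be in the SAP.
- **That joint power is 0.85 × 0.85 if both must succeed.** That product gives eradication the full 85% which the design does not secure. The right bound is eradication's own reduced power.

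The amendment clause bears on pathogen numbers, but without a number or a trigger it does not restore the power.

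**Conclusion.** The point holds as a mismatch between the stated sample size and one of the two endpoints it appears to cover, together with an unnamed primary endpoint. For the difference that justifies 200 per group, eradication has less than 85% power at any culture yield below 100%. That conclusion needs no outside figure.

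The amounts are illustrative. They rest on an assumed effect (90% vs 79.2%), an assumed yield (30% to 70%) and an assumed two-sided test. On those terms power is 37% to 71%, and the detectable difference is 22.0 to 13.3 points instead of 10.8. The effect on the error rate or on joint power depends on a success rule that the protocol does not state. A SAP could add testing detail, but the basis of the sample size is fixed in this protocol and should be corrected there.

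**What to change.** In section VIII and Protocol Summary items 11 and 13:
1. Name clinical response at Visit 3 (2–4 days after therapy) as the single primary endpoint, and say that the 200 per group rests on it.
2. Make eradication secondary, tested at 0.05 only if the primary comparison succeeds.
3. State the number expected to have a baseline pathogen, and give eradication's power or confidence-interval width for that number.

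This costs protocol wording only, with no extra subjects or procedures. The downside is that the stated power for eradication becomes lower and eradication can no longer carry the claim alone.

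Other structures are legitimate but cost more. Splitting alpha to 0.025 each needs 240 per arm for 85% power at the same assumed effect (200 per arm gives 77%), before any allowance for culture-negative subjects. Requiring both endpoints to succeed would mean sizing the trial on the culture-positive number.

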### B. Inclusion Criteria

Subjects may be included in the study if they satisfy all of the following criteria:

1. Age: 18 years of age or older
2. Sex: male or female
3. Clinical picture consistent with pneumonia, including at least two of the following clinical signs or symptoms of pneumonia:
  - cough
  - fever (101°F or greater)
  - production of purulent sputum
  - rales
  - pleuritic chest pain
4. Chest x-ray infiltrate compatible with acute infection
5. If female, subject must be using an acceptable form of birth control and have a negative pregnancy test prior to being enrolled; or be post-menopausal
6. Must be able to give informed consent

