## **D. Patient Recruitment and Screening Procedures**

Subjects who meet all the inclusion criteria and exhibit none of the exclusion criteria may be enrolled. A Potential Subject Roster, which will document the initials of each patient considered for study entry, the date of assessment, severity of diagnosis and the reasons for not enrolling any potential study subject, will be maintained at each site.

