### **A. Visit #1 - Baseline Visit**

At the baseline visit, the following will be performed:

1. Sign informed consent form
2. Pertinent medical history
3. Pertinent physical examination, including vital signs
4. Chest x-ray (PA & lateral)
5. Respiratory secretions must be obtained within the 48 hours prior to study entry for routine culture and Gram stain. Deep expectorated or auctioned sputum, transtracheal aspirates, bronchial brushings, washings, biopsies, or pleural fluid are

all acceptable. Specimens should also be cultured for *M pneumoniae*, *L. pneumophila*, and *C pneumoniae* when indicated and if the microbiology laboratory has the capability to perform these cultures.

Disk and MIC susceptibilities for all study drugs are to be performed on all aerobic pathogens isolated (except *M pneumoniae*, *L. pneumophila*, and *C pneumoniae*). Genus and species identification is required on all pathogens isolated.

6. Obtain venous blood samples and process blood at local institution:
  - a. Hematology:
    - hemoglobin
    - hematocrit
    - RBC
    - platelet count
    - WBC, including differential
  - b. Serum chemistry:

-glucose	-total bilirubin
-creatinine	-inorganic phosphorous
-BUN	-alkaline phosphatase
-total protein	-calcium
-albumin	-uric acid
-sodium	-chloride
-potassium	-CO 2
-SGOT	-LDH
-SGPT	
  - c. Pharmacokinetics (these will be shipped and analyzed at a central laboratory, see Appendix II for instructions)
7. Urinalysis, including pH, specific gravity, and microscopic examination of sediment for RBC, VIBC, and non-amorphous crystals
8. Urine pregnancy test
9. Evaluate subject for signs and symptoms of pneumonia
10. Complete confidential follow-up form
11. Assign subject number
12. Pharmacist to open randomization envelope and dispense/prescribe appropriate drug

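### Section VIII fixes an unadjusted chi-square although prognostic baseline values are already collected; adjusting for them is an optional, modest gain in precision

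*Protocol*

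**What the plan says.** Protocol Section VIII gives one efficacy method: "A Chi-square analysis will be performed to compare the rates of eradication and response between the two drugs". The sample-size sentence follows: "Using an alpha level of 0.05 and power of 85% will require a sample size of 200 subjects in each of the two groups". Neither sentence mentions a covariate, a stratum or an adjusted model.

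The design does not balance prognosis either. Under E. Randomization, "This randomization schedule will provide for equal numbers of subjects in the two regimens", and for each qualifying subject "the next available randomization envelope in the sequence will be opened to reveal the appropriate therapy regimen". No stratification by severity or age is described.

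Baseline information is nevertheless available:

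- Age is an eligibility item ("Age: 18 years of age or older") and enters the creatinine clearance formula under Dosage Adjustment.
- Visit #1 includes vital signs, hematology with WBC, serum chemistry with BUN, and the item "Evaluate subject for signs and symptoms of pneumonia".
- Severity of diagnosis is mentioned in Section 2.2.D, where a roster holding "the date of assessment, severity of diagnosis and the reasons for not enrolling any potential study subject, will be maintained at each site". No scale is defined, and severity appears neither in the Visit #1 list nor in the Appendix I flow chart.

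**The concern.** When a baseline value predicts a yes/no outcome, part of the outcome's variance is explained before treatment starts. A crude two-by-two comparison leaves that part in the standard error. It also leaves in the estimate whatever difference in baseline risk chance has put between the arms. Standardizing over baseline values removes both and still estimates the same overall difference in response rates, from the same subjects.

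Here neither the allocation nor the stated analysis uses baseline prognosis, although the data would be on hand. What is at stake is some precision and power. The validity of the test is not at stake.

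**Working it through.** **1. The plan's own figure.** Section VIII gives alpha 0.05, power 85% and 200 per group, but no response rates, difference, margin or sidedness. The figure of 200 can therefore only be back-solved. Starting from 90% (the background success rate for Drug A, which is not a design input), a two-sided test without continuity correction at 200 per group detects a fall of 10.8 points or a rise of 7.3 points. A one-sided test with continuity correction of 90% against 80% needs 202. A non-inferiority design at 90% in both arms, with a 9-point margin and one-sided 0.025, needs 200. Several designs fit and none is confirmed, so the stated 85% is taken as the starting point.

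**2. Gain from adjustment.** The share of outcome variance explained by baseline risk is

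R² = Σ wₖ(pₖ − p)² / [p(1 − p)], with p = Σ wₖpₖ.

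Adjustment multiplies the variance of the difference by about (1 − R²). With two-sided 0.05 (assumed), power becomes Φ[(1.960 + 1.036)/√(1 − R²) − 1.960]. The saving in subjects at equal precision is 400 × R².

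The documents give no risk distribution. Assume three baseline-risk levels holding 40%, 40% and 20% of subjects:

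| Response by level (%) | p | R² | Power from 85% | 400 × R² |
|---|---|---|---|---|
| 93 / 90 / 85 | 0.902 | 0.0097 | 85.3% | 4 |
| 95 / 90 / 78 | 0.896 | 0.0415 | 86.4% | 17 |
| 95 / 88 / 72 | 0.876 | 0.0650 | 87.3% | 26 |
| 97 / 90 / 70 | 0.888 | 0.0987 | 88.4% | 39 |

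Last row in full: p = 0.4 × 0.97 + 0.4 × 0.90 + 0.2 × 0.70 = 0.888. The between-level variance is 0.4 × 0.082² + 0.4 × 0.012² + 0.2 × 0.188² = 0.00982. The total is 0.888 × 0.112 = 0.09946, so R² = 0.0987. The standard error of the difference falls from √(2 × 0.09946/200) = 0.0315 to √(2 × 0.08964/200) = 0.0299.

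**3. A two-level version.** Suppose 30 to 50% of subjects are higher-risk and respond 10 to 20 points less often than the 95% assumed for the rest. Then R² is 0.03 to 0.09, inside the range above.

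**4. Size of chance imbalance.** The between-arm difference in the higher-risk share has SD √[2q(1 − q)/200], which is 4.6 points at q = 0.30 and 5.0 points at q = 0.50. In the two-level settings a 1.96-SD imbalance shifts the crude difference by 0.9 to 2.0 points, against a crude standard error of 2.7 to 3.6 points.

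**5. Check by simulation.** With 40,000 trials per setting, 200 per arm and a binary risk factor (four assumed settings), the crude chi-square had type I error of 4.6 to 4.9%. A Cochran-Mantel-Haenszel test stratified on the factor had 4.7 to 5.0%. At an 11-point true difference, stratifying raised power by 0.4 to 2.1 points (for example 87.2% to 87.6%, and 86.8% to 88.9%).

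**The case against.** The strongest reply is that nothing here is wrong. Allocation is randomized 1:1, the chi-square holds its error rate, and chance imbalance averages to zero and is already covered by the 5% alpha. Covariate adjustment is commonly left to the analysis plan, which is not at hand, and Section VIII does not exclude an adjusted or sensitivity analysis. The gain rests entirely on assumed inputs. The population is also narrower than the adult age range suggests: the Protocol Summary limits it to outpatients suited to oral treatment, and severe renal failure and neutropenia are excluded. That makes the larger scenarios less plausible; the top one needs a 27-point gap between the best and worst risk levels.

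All of this stands, and it limits the point to an efficiency suggestion. What remains is that the protocol itself names the less efficient method as its efficacy comparison, while usable baseline values need no new procedure.

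Two stronger readings are tempting and are not supported. A reader might infer that leaving severity out biases the comparison; the random allocation and the type I error in the check speak against that. A reader might also infer that a severity grade is ready to be copied from the roster, or that without it no baseline prognosis can reach the analysis. The roster has no defined categories, and the Visit #1 values can be used without it.

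**Conclusion.** The point holds as an optional efficiency improvement. Under the assumed prognostic strengths, adjustment lowers the variance by roughly 1 to 10%. That is worth about 0.3 to 3.4 power points from 85%, or about 4 to 39 of 400 subjects. If the baseline values predict response only weakly, the gain is negligible. The range assumes a two-sided 0.05 test, overall response near 88 to 90%, and that the chosen covariates together separate risk about as well as the three-level index. The documents supply none of these as design inputs. No size can be given for eradication, because the documents give neither an eradication rate nor the number of subjects expected to have a pathogen isolated.

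**What to change.** In Section VIII, make the main comparison of clinical response and of eradication a baseline-adjusted difference in proportions with a confidence interval, for example from logistic regression with marginal standardization. Prespecify age and a few Visit #1 values, chosen from signs and symptoms, vital signs, WBC and BUN. Keep the chi-square as a supportive analysis. The list should be short: at 90% response, 400 subjects give only about 400 × 0.10 = 40 non-responders.

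Optionally, if severity of diagnosis is to be a covariate, define common categories and record it on the Visit #1 case report form before the randomization envelope is opened.

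The cost of the main change is a revised sentence and an agreed covariate list, with no new procedure for subjects. Using severity costs more: a scale must be chosen, one form field added, and the same categories applied at all of the 20 to 25 sites.
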